## 5 Study Subjects – Enrollment and Withdrawal

- Accrual Goal: Goal of 10 patients (e.g. 20 legs) within 18 months to complete 6-month follow up of all patients in 2 years. Goal is based upon study being a pilot study. Previous studies have performed 18 legs (9 patients) and did serve as a baseline for our study. After discussions with 2 surgeons at the University of Wisconsin with clinical expertise in performing fasciotomy and fasciectomy, it has been determined that they will anticipate seeing over 15 of these patients in the next year the majority of whom are otherwise healthy and would meet inclusion and exclusion criteria to be eligible for the study. Providing some of these individuals will not wish to participate in the study or otherwise be excluded, 18 months provides a realistic goal accrual period.

- Screening will be performed at initial diagnosis prior to enrollment and prior to first injection. At the time of injection, investigator will review contraindications with participant including local infection, known hypersensitivity to botulinum toxin, neuromuscular disorder, dysphagia, breathing difficulties, and pregnancy.

## 5.1 Subject Population

Subjects will be greater than or equal to 18 years of age at the time of enrollment with no upper limit of age provided the subject meets inclusion criteria. There will be no limitations on enrollment based on race or ethnicity of the subject. Female subjects of childbearing potential will be screened for pregnancy prior to enrollment with urine pregnancy test.

## 5.2 Inclusion Criteria

Inclusion Criteria	
1	Willing to provide written informed consent
2	Willing to comply with all study procedures and be available for the duration of the study
3	Male or female, at least 18 years of age
4	Documented diagnosis of R-CECS determined with elevated compartmental pressure testing following lower extremity fascia release (fasciotomy or fasciectomy)
5	Females of childbearing potential must have a negative urine pregnancy test prior to enrollment and agree to use adequate contraception (hormonal or barrier method of birth control; abstinence) prior to randomization, for the duration of study participation, and for 7 days following completion of therapy. 
 
• A female of child-bearing potential is any woman (regardless of sexual orientation, having undergone a tubal ligation, or remaining celibate by choice) who meets the following criteria:               
 
◦ Has not undergone a hysterectomy or bilateral oophorectomy; or
 
 
 
• Has not been naturally postmenopausal for at least 12 consecutive months (i.e., has had menses at any time in the preceding 12 consecutive months).
 

## 5.3 Exclusion Criteria

Exclusion Criteria	
1.	History of hypersensitivity or allergy to any of the study drugs or drugs of similar chemical classes
2.	Known neuromuscular disease
3.	Known pulmonary disease including but not limited to asthma, pneumonia, or upper respiratory tract infection
4.	Dysphagia
5.	Known cardiac disease including but not limited to congestive heart failure, arrhythmia, or history of myocardial infarction
6.	Enrolled in another clinical trial or has used of any investigational drugs, biologics, or devices within 30 days prior to enrollment
7.	Currently or have taken in the past medications that affect neuromuscular function, aminoglycosides, muscle relaxants, or other botulinum neurotoxin agents. Currently taking any blood-thinning medications including, but not limited to Plavix, Coumadin, Eliquis, Xarelto
8.	Women who are pregnant or breast-feeding
9.	Vulnerable populations
10.	Not suitable for study participation due to other reasons at the discretion of the investigator

## **5.4 Subject Screening for Recruitment**

### **5.4.1 Subject Identification**

Potential subjects will be identified at the time of diagnosis by the investigators. Using their clinical discretion, discussion of the study will be offered alongside current standard treatments. Should the participating be interested in participation, the written consent form will be provided and clinic appointments scheduled with study staff for enrollment. Participant name and contact information will be provided to study staff by the diagnosing investigator for further contact with the study team.

Prior to enrollment, primary investigator will discuss via telephone call the timeline, interventions, goals, potential side effects, and incentive of the study. Subjects will also be screened for inclusion and exclusion criteria prior to enrollment. If more discussion is desired by potential subjects, co-investigators can contact potential subjects by telephone prior to scheduled enrollment. Eventual enrollment in the study will be elective provided the subject meets inclusion criteria.

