### **5.4.2 Recruitment and Retention Strategies**

Investigators have practice specialties of sports medicine, vascular surgery, and pain medicine that lend themselves to identifying potential subjects in clinic. As this is a pilot study, there will be no differentiation amongst sexes, races, or ethnicities and simply the first ten individuals enrolled and undergoing treatment will be the group studied.

Retention strategies include incentives provided at the time of injection, 2-month follow up, and 6-month follow up. Incentive will consist of \$100 at the time of injection, and \$50 at each the 2-month and 6-month follow up for a total of \$200. Second retention measure is telephone follow up for the 4 and 6-month follow ups in lieu of clinic visit

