### **6.8 Randomization and Blinding of Study Drug**

The subjects and drug will not be blinded in this study and subjects will not be randomized into differing treatment arms.

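### The study is offered at the investigator's discretion before eligibility screening and patients not offered it are not recorded, so any selection into this single-arm pilot cannot be measured

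*Combined protocol and SAP*

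**What the plan says.** Section 5.4.1 has the investigators identify patients at diagnosis and leaves the offer to their judgement: "Using their clinical discretion, discussion of the study will be offered alongside current standard treatments". It then describes the consent form, scheduling, a telephone call and screening against the inclusion and exclusion criteria, in that order.

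Section 5.4.2 defines the sample: "simply the first ten individuals enrolled and undergoing treatment will be the group studied". Section 8.3 analyses everyone injected. Section 5.3 has an open-ended last criterion, exclusion 10: "Not suitable for study participation due to other reasons at the discretion of the investigator".

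On patient flow, section 5 sets a "Goal of 10 patients (e.g. 20 legs) within 18 months". It reports that two surgeons said "they will anticipate seeing over 15 of these patients in the next year", and it expects more than half of them to be eligible. It also allows that "some of these individuals will not wish to participate in the study or otherwise be excluded".

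There is no comparator; section 6.8 states that "subjects will not be randomized into differing treatment arms". The only log of patients described is the enrollment log in 9.1.1, which links enrolled subjects to their study numbers.

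**The concern.** A first-ten rule suggests a consecutive series, but it counts only patients who were told about the study. An eligible patient who is never approached is not screened, not counted and not mentioned in the results. Section 5.4.2 names three specialties that will identify patients, and no common rule for approaching them is given.

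The primary objective (section 3) is efficacy, and section 8.1 says the pilot will supply effect sizes to power later studies. Those effect sizes are changes from baseline in the ten treated patients. If the patients approached tend to be those expected to do better, the mean change is too large for R-CECS patients in general, and a later study planned on it would be too small. Comparing each patient with their own baseline does not prevent this, because the selection acts on the size of the change. Without a record of those not approached or declining, the pilot also cannot report what share of eligible patients take part, which is useful when planning a larger study.

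**Working it through.** **1. Where each safeguard acts.** The order in 5.4.1 is diagnosis, discretionary offer, screening, enrolment. The first-ten rule (5.4.2) and the all-injected analysis set (8.3) apply at or after enrolment. They prevent choosing ten from a larger enrolled group, or dropping treated patients. Neither controls the offer. The log in 9.1.1 also starts at enrolment.

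**2. How many candidates there may be.** Section 5 gives over 15 patients seen in a year and an 18-month accrual period. If that rate continues, 15 × 1.5 = 22.5 patients are seen; this is a floor, since the text says over 15. Section 5 then reduces the figure without giving numbers: a majority are eligible, and some refuse or are excluded. I assume a range.

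| Eligible (assumed) | Eligible pool | Uptake needed for ten |
|---|---|---|
| 51% | 22.5 × 0.51 = 11.5 | 10 / 11.5 = 87% |
| 70% | 22.5 × 0.70 = 15.75 | 10 / 15.75 = 63% |
| 90% | 22.5 × 0.90 = 20.25 | 10 / 20.25 = 49% |

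At 70% eligible and 70% uptake the pool is 15.75 × 0.70 = 11.0, one more than the places available. At 51% and 80% it is 9.2, which leaves no room for choice.

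**3. Possible shift in the mean change.** If a fraction p of candidates is taken, and the investigator's ranking correlates r with the eventual pain decrease, the mean shifts by r × i × SD. Here i = φ(z)/p and z = Φ⁻¹(1 − p). The documents give no r; I take 0.3. Section 8.1 gives SD = 1.

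| Taken / pool | p | i | Shift at r = 0.3 | Points at SD 1 |
|---|---|---|---|---|
| 10 / 11 | 0.909 | 0.180 | 0.05 SD | 0.05 |
| 10 / 12 | 0.833 | 0.300 | 0.09 SD | 0.09 |
| 10 / 15 | 0.667 | 0.545 | 0.16 SD | 0.16 |
| 10 / 22.5 | 0.444 | 0.889 | 0.27 SD | 0.27 |

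The formula is for a large pool. Simulating the best-ranked ten from pools of 11, 12, 15 and 22 at r = 0.3 gives 0.05, 0.08, 0.15 and 0.25 SD, so the approximation is adequate.

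**4. Sensitivity.** For r from 0.1 to 0.5 the shift is 0.1 × 0.180 = 0.02 to 0.5 × 0.180 = 0.09 SD at 10 of 11, and 0.09 to 0.44 SD at 10 of 22.5. The shift in points is proportional to the SD of the change. The plan does not say clearly whether its SD of 1 is that of the change or of the score, so using it for the change is an assumption. An SD of 2 would double every figure in the last column.

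**The case against.** The strongest reply is that there may be hardly any choice to make. The 22.5 counts patients seen, and section 5 relies on ineligibility and refusal to explain why 18 months is realistic for ten. If nearly every willing, eligible patient is needed, the shift is close to zero. This stands, and it is why 0.27 SD is the extreme case: it requires every patient seen to be eligible and willing.

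Three stronger readings are tempting, and the documents support none of them.

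- A reader might infer that the ten will be hand-picked likely responders. No predictor of response is named, no published use in R-CECS is reported, and no intention to select is expressed. Sections 2.1 and 2.5 report earlier clinical success for the PI only, not for the investigators as a group.
- A reader might infer that about 22 candidates will compete for ten places. That ignores the reductions stated in section 5 itself.
- A reader might infer that a control arm would reveal the problem. Randomisation would balance prognosis between arms. It would not show that the enrolled patients respond better than others, because both arms would come from the same selected pool. Only a record of patients not enrolled can show that.

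It is also fair to say that section 5 places screening at initial diagnosis and that 7.4.1 has the study discussed with the PI at the pressure-measurement visit. Both read as routine, and the discretion in 5.4.1 may be no more than exclusion 10 applied at first contact. Even so, neither section requires that every eligible patient be offered the study, or that a reason be kept when one is not. Limited generalisability is inherent in a ten-patient, single-centre, open-label pilot, and acceptance rate is not a stated objective. Those points limit the severity but do not remove the gap.

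**Conclusion.** The point holds as a gap in control and recording. The offer is discretionary, 5.4.1 describes it ahead of screening, nothing in the plan governs who receives it, and no trace is kept of those who do not. Any selection on expected outcome would bias the mean change, and neither its presence nor its size could be established afterwards.

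Whether selection would occur is unknown. At r = 0.3 and SD 1 the bias runs from 0.05 to 0.27 points, or 3% to 13% of the 2-point target (0.05/2 and 0.27/2). It would be nil if every willing, eligible patient is needed. The range rests on an assumed correlation, on the yearly rate continuing, and on the plan's SD applying to the change. The change is worth making because it is cheap and because the missing record could not be rebuilt reliably after enrolment.

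**What to change.** In 5.4.1, replace the discretionary offer with wording such as: Every patient diagnosed with R-CECS who meets 5.2 and 5.3 is offered the study, in order of diagnosis, until ten have been injected. Keep exclusion 10, and record the reason each time it is used.

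Add a screening log, under IRB approval, with one line per diagnosed patient: sequence number, eligible or not, offered or not, accepted or not, and reason. It should hold no identifiers or dates, because it covers people who have not signed the authorization described in 5.6.3. Report the numbers diagnosed, eligible, offered and treated beside the primary result.

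The cost is a protocol amendment and a log of roughly 22 lines if the expected rate holds. Investigators must state a reason under exclusion 10 instead of simply not raising the study. Some discretion remains through that criterion, but it becomes visible. Treatment, sample size and analysis do not change.

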### **5.4.2 Recruitment and Retention Strategies**

Investigators have practice specialties of sports medicine, vascular surgery, and pain medicine that lend themselves to identifying potential subjects in clinic. As this is a pilot study, there will be no differentiation amongst sexes, races, or ethnicities and simply the first ten individuals enrolled and undergoing treatment will be the group studied.

Retention strategies include incentives provided at the time of injection, 2-month follow up, and 6-month follow up. Incentive will consist of \$100 at the time of injection, and \$50 at each the 2-month and 6-month follow up for a total of \$200. Second retention measure is telephone follow up for the 4 and 6-month follow ups in lieu of clinic visit

## **5.5 Vulnerable Populations**

Vulnerable populations will not be included in this study.

### **5.5.1 Subject Capacity**

Subjects must have the capacity to provide informed consent as determined by the PI and study team.

### **5.5.2 Subject/Representative Comprehension**

Prior to providing written consent, investigator will ask that subjects recall and restate what they have been told during the informed consent process to ensure comprehension. Further, teams will follow state laws and institutional policies to determine who will serve as legal authorized representative (LAR) and that research teams will include these LARs to the extent possible in the consent process.

## **5.6 Informed Consent**

Study staff will be responsible for ensuring that valid written consent is obtained and documented for all subjects.

### **5.6.1 Process of Consent**

- Written informed consent will be obtained by the physician performing the Botox injection prior to injection being performed.
- Consent to perform the injection will be performed on the standard UW Health Botulinum Toxin Injection Consent Form (301647-DT) available on UConnect. Consent for participation in the study will also be signed prior to enrollment.
- Informed consent will be obtained in person by competent individuals making witness signature unnecessary.

- Investigator will review the consent form with the subject and obtain written consent prior to performing Botox injection at the time of the first clinic visit (time 0). For individuals that are non-English speakers, a translator will be present to review consent in the same manner as with subjects who speak English.

### **5.6.2 Consent Form (see templates for UW-Madison)**

**Please see supporting documents**

### **5.6.3 HIPAA**

Information about study subjects will be kept confidential and managed according to the requirements of the Health Insurance Portability and Accountability Act of 1996 (HIPAA). HIPAA documentation will be integrated into the consent form (Appendix 2). Attached as part of our application is a signed subject authorization form that includes:

- What protected health information (PHI) will be collected from subjects in this study
- Who will have access to that information and why
- Who will use or disclose that information
- The rights of a research subject to revoke their authorization for use of their PHI.

### **5.6.4 Revoking Consent**

In the event that a subject revokes authorization to collect or use PHI, the investigator, by regulation, retains the ability to use all information collected prior to the revocation of subject authorization. For subjects that have revoked authorization to collect or use PHI, attempts should be made to obtain permission to collect at least vital status (i.e. that the subject is alive) at the end of their scheduled study period.

### **5.6.5 Costs to the Subject**

There will be no cost to subjects for the clinic visits or procedures that are done for research purposes only and are not part of subject's regular care. These services will be paid for via Division of PM&R research grant.

Subjects will have to pay for basic expenses like any childcare, food, parking, or transportation related to study activities. Study will also not provide compartment pressure measurements.

If treatment for side effects is needed while in the study, the subject or subject's insurance will be financially responsible for this treatment.

### **5.6.6 Payment for Participation**

For completion of all the study visits, subjects will receive a total of \$200 for completing in this study.

- We will give \$100 for receiving the Botox injection, obtaining baseline strength measurements, and filling out the UWRI questionnaire.
- We will then provide \$50 after having strength measurements repeated at 2 months and following up with physician for monitoring of side effects and completion of UWRI.
- Final \$50 will be mailed to the participant after the 6-month telephone call for completing the study.
- If subject chooses to leave or we take subject off the study for any reason, they will be allowed to keep the money already given them.

Enrollment of individuals with a potential status relationship, including family members of the research team, will be declared in an application to the IRB (Initial Review Application, Change of Protocol) and justification for the

inclusion of these subjects provided. The IRB will then assess on a case-by-case basis whether the inclusion is warranted by the protocol, the recruitment and consent process are free from undue influence, and the confidentiality of these subjects will be protected adequately.

## **5.7 Early Withdrawal of Subjects**

### **5.7.1 Premature termination of study**

This study may be temporarily suspended or prematurely terminated if there is sufficient reasonable cause. Written notification, documenting the reason for study suspension or termination, will be provided by the suspending or terminating party to the Division of PM&R and regulatory authorities. If the study is prematurely terminated or suspended, the PI will promptly inform the IRB and will provide the reason(s) for the termination or suspension.

Circumstances that may warrant termination or suspension include, but are not limited to:

- Determination of unexpected, significant, or unacceptable risk to participants
- Demonstration of efficacy that would warrant stopping
- Insufficient compliance to protocol requirements
- Data that are not sufficiently complete and/or evaluable
- Determination of futility

Study may resume once concerns about safety, protocol compliance, data quality are addressed and satisfy the sponsor, IRB and/or FDA.

### **5.7.2 When and How to Withdraw Subjects**

As the study involves a one-time injection, subjects will be withdrawn of their own volition or by failure to adhere to protocol requirements.

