#### Withdrawal

- Patients who wish to withdrawal from the study may do so by verbal or written request to the investigator. Or they may indicate withdrawal by failure to follow up with study protocol.

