### **5.7.3 Data Collection and Follow-up for Withdrawn Subjects**

Intervention is a one-time injection. Therefore, patients who opt out of the study will not be able to opt out of treatment once injection is performed.

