### **6.7 Prior and Concomitant Therapy/ Standard of Care**

Patient will not undergo concomitant medical therapy including, but not limited to physical therapy or surgical fasciotomy. If the patient has undergone previous physical therapy for the same diagnosis, this data will be collected but will not alter ability to participate in the study. Allowed in the study are over-the-counter pain medications including NSAIDs and Tylenol as needed.

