#### 8.2 Statistical Methods

Basic descriptive statistics, means (SD) and medians (IQR) for continuous variables and frequencies (percentages) for categorical variables will be used to summarize patient outcomes. For the primary outcome, change in pain (from baseline on 0-10 numeric rating scale) will be assessed at each time point (2,4,6 months) using Friedman's ANOVA. Friedman's ANOVA is the non-parametric analog to one-way repeated measures ANOVA and is often

used for ordinal outcomes. If necessary and feasible, GEE models will be constructed to further assess changes in pain while accounting for intra-subject correlation. Secondary endpoints utilizing the UWRI will also be assessed in this manner. Change in strength outcomes at baseline and 2 months will be assessed using Wilcoxon signed rank tests or, if necessary, linear mixed effects models for repeated measures, to account for intra-subject correlation (left and right legs).

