### **8.3 Subject Population(s) for Analysis**

The subject population for analyses will include all patients who receive the Botox injection. We intend to minimize loss to follow-up; however, if patients drop out of the study, we will attempt to use statistical methods that allow for missing outcomes (e.g. GEE/Linear models for repeated data) so that all available data can be used for analysis.

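### Withdrawal for non-adherence, with no outcome collection afterwards, can lose 4- and 6-month pain data from patients still in pain and so overstate relief

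*Combined protocol and SAP*

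**What the plan says.** Section 5.7.2 notes that treatment is one injection, then states that "subjects will be withdrawn of their own volition or by failure to adhere to protocol requirements". The Withdrawal item in section 2.7.2 says of patients who wish to leave: "Or they may indicate withdrawal by failure to follow up with study protocol". Section 6.7 sets the restriction: "Patient will not undergo concomitant medical therapy including, but not limited to physical therapy or surgical fasciotomy". Over-the-counter analgesics are allowed.

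Section 5.7.3 is headed as covering data collection and follow-up for withdrawn subjects, but its only content is that "patients who opt out of the study will not be able to opt out of treatment once injection is performed". The one contact after a subject leaves that appears elsewhere is vital status after a subject revokes authorization to use health information (section 5.6.4). That is not an outcome.

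On analysis, section 8.3 states: "The subject population for analyses will include all patients who receive the Botox injection". If patients drop out, "we will attempt to use statistical methods that allow for missing outcomes", with GEE and linear repeated-measures models as examples, "so that all available data can be used for analysis". Under section 8.2 the primary outcome "will be assessed at each time point (2,4,6 months) using Friedman's ANOVA", and GEE follows only if needed and feasible. The study summary and section 6.8 confirm that there is no comparator and no randomization.

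**The concern.** Every subject enters with disease that has recurred after fascial release. Those most likely to turn to physical therapy or further surgery are those whose pain the injection did not relieve. If seeking such treatment counts as non-adherence, the plan permits their withdrawal and provides no later pain score. The 4- and 6-month data would then come disproportionately from patients who did well.

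The injection is given once, at time 0. What a subject does afterwards may complicate interpretation of later pain scores, but it is no reason to stop collecting them.

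Section 8.1 says that the trial is to supply effect sizes at each time point for planning later studies. Overstated relief would carry into those calculations, and no control arm is available to show it.

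**Working it through.** **The plan's own figures.** Section 8.1 assumes a 2-point fall with SD 1, 80% power with 6 patients, and 15% dropout. With four time points, a linear fall and a two-sided alpha of 0.05 (pattern and alpha assumed), a one-way ANOVA with 6 patients per time point has 80.2% power. Then 6/0.85 = 7.06. Dividing by an assumed Friedman efficiency of 0.955 × 4/5 = 0.764 gives 9.24, hence 10 patients. The sample size reproduces and does not decide this point. It matters here because 15% is the only dropout rate that the plan gives, and no reasons for dropout are stated. Even with purely random dropout, the chance of losing at least 2 of 10 patients is 1 - 0.85^10 - 10 × 0.15 × 0.85^9 = 46%.

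**Bias identity.** With loss fraction d, the available-case mean differs from the full mean by

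bias = d × (mean relief in retained - mean relief in lost).

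The documents do not give the gap in relief. For gaps of 1, 2 and 3 points at d = 0.15, the bias is 0.15, 0.30 and 0.45 points. With 2 of 10 lost it is 0.2, 0.4 and 0.6.

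**Mixture model (assumed).** Responders fall 3 points, non-responders 0, each with SD 1. With 70% responders and half of the non-responders lost, d = 0.30 × 0.5 = 0.15.
- True mean: 0.70 × (-3) = -2.1. Observed: -2.1/0.85 = -2.47, about -2.5. The bias is about 0.4 points.
- P(fall of 2 or more) is 0.841 for responders and 0.023 for non-responders. True share: 0.70 × 0.841 + 0.30 × 0.023 = 60%. Observed: (0.70 × 0.841 + 0.15 × 0.023)/0.85 = 70%.

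**Single-population model (assumed).** Mean relief 2, SD 1, correlation r between visits. Patients with less than 2 points of relief at month 2 (half of all) are lost with probability 0.3, so d = 0.15. Mean month-6 relief in the lost group is 2 - 0.798r, so the bias is 0.15 × 0.798r/0.85: 0.07 at r = 0.5 and 0.11 at r = 0.8. At 25% loss it is 0.13 to 0.21. If true mean relief is 0 or 1, most patients fall below the 2-point cut, loss is closer to random, and the bias at 13 to 15% loss is only 0.00 to 0.03.

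**No drug effect (assumed).** Between-patient SD 1.5 and visit SD 1, so the change has SD √3.25 = 1.80 and r = 2.25/3.25 = 0.69. Patients who are worse at month 2 leave with probability 0.3 (15% loss overall). The observed mean is about -0.17, and false improvement occurs in about 4.5 to 5% of trials, against a nominal one-sided 2.5%.

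**What the section 8.3 models recover.** In the single-population model with mean relief 2, an estimate valid under missing at random has bias of about 0 when loss depends only on the recorded month-2 score. When loss depends on a month-4 score that is never collected, the remaining bias is 0.02 to 0.04 at 15% loss and 0.04 to 0.07 at 25%. Unweighted GEE generally needs data missing completely at random, which loss driven by pain violates. Friedman's test in its standard form needs a complete set of visits, so a patient without months 4 and 6 leaves the primary test.

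**The case against.** No section says that starting physical therapy or having surgery leads to withdrawal. Section 5.7.2 is one generic sentence, and section 11.2 handles participant noncompliance as a protocol deviation, to be reported and corrected, without mentioning withdrawal. This stands: the link is an inference from 5.7.2 and 6.7 read together. But 5.7.2 is worded as a rule, and nothing in 11.2 exempts barred treatment from it.

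A reader might infer from section 2.7.2 that one missed contact is a withdrawal. The text does not support that. It describes how patients who wish to leave may signal it, and it gives no number of missed contacts.

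Section 8.3 keeps all injected patients and names linear repeated-measures models, which need only missing at random. In the illustrations above such a model removes most of the bias. This also stands, but section 8.3 promises only an attempt, the primary test is Friedman's, and no sensitivity analysis for outcome-related loss is named.

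Retention is supported by staged payments, the last after the 6-month call, and by telephone contacts at 4 and 6 months (section 5.4.2). That lowers the risk of ordinary loss. It does not govern a subject whom the study itself withdraws.

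**Conclusion.** The point holds as a risk. The withdrawal rule, the treatment restriction and the absence of outcome collection after withdrawal together allow 4- and 6-month pain data to be lost in relation to outcome. Where that happens, the direction is toward greater apparent relief, and the planned analysis corrects it only in part.

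A reader might infer that non-responders will drop out and that the result will be badly inflated. The documents do not support this. They give no rate of other treatment and no pain level for lost patients. Large distortions, such as a spurious mean fall of 1.0 point with 20% false positives under no drug effect, require about half of the patients to be lost, against the planned 15%.

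At 15% loss the illustrations run from about 0.1 to 0.2 points in single-population models (close to zero if nearly all patients are non-responders) to about 0.4 points in the mixture with 70% responders. These are available-case figures, and all are well below the 2-point endpoint. A change is still worth making, because the trial's product is an effect size and the remedy is cheap.

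**What to change.** - In sections 5.7.2 and 5.7.3, separate non-adherence from stopping data collection. Attempt the scheduled 2-, 4- and 6-month pain and UWRI contacts for every injected subject unless the subject withdraws consent.
- In section 2.7.2, state that a missed contact is re-tried and is not by itself a withdrawal.
- Reconcile 5.7.2 with 11.2, so that it is clear whether a departure from 6.7 is a deviation, a withdrawal or both.
- Record the type and date of any physical therapy or surgery.
- In section 8, use all collected values in the main analysis and pre-specify a sensitivity analysis. One option is to count subjects who are lost or otherwise treated as non-responders.

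None of this changes which concomitant treatments are allowed. The cost is protocol wording and a few telephone calls that are already in the schedule. The estimates may come out slightly less favourable.
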